### **Background**

The acquisition of pancreatic tissue is a critical step in the diagnosis and treatment of pancreatic diseases and has been included in several international guidelines for pancreatic disease management. Commonly used techniques include open or laparoscopic biopsy, image-guided percutaneous biopsy, and endoscopic ultrasound-guided biopsy. It is essential to establish a pathological diagnosis of the tumor before initiating non-surgical or neoadjuvant therapy. Currently, endoscopic ultrasound (EUS) and ultrasound (US)-guided pancreatic biopsies are recommended as first-line methods for obtaining samples from focal pancreatic lesions. Both methods demonstrate excellent diagnostic performance and are associated with a low incidence of adverse events. EUS-guided pancreatic biopsy, including fine needle aspiration (FNA) and fine needle biopsy (FNB), has become the preferred technique due to its high patient tolerance and low risk of complications. In contrast, image-guided percutaneous biopsy techniques, such as FNA or core needle biopsy (CNB), can obtain more histological specimens for molecular biological testing and genetic testing. Currently, there are no randomized controlled trials directly comparing the effectiveness and safety of these two methods, and most of the previous related studies are single-center, retrospective studies with low evidence strength. Therefore, it is imperative to conduct large-scale, multicenter clinical studies to provide high-quality evidence for the clinical application of both techniques, thereby offering a research basis for formulating individualized pancreatic biopsy protocols.

### **Objective**

It is proposed to conduct a retrospective, multicenter, propensity score-matched study to compare the differences in diagnostic inaccuracy, complication rates, and the risk of repeat biopsy between EUS and US-guided pancreatic biopsy techniques for focal pancreatic diseases.

### **Protocol**

Study Period: January 1, 2017, to December 31, 2023, retrospective study. Study Location: Seven tertiary Grade A hospitals in China: The First Affiliated Hospital of Zhejiang University School of Medicine, Zhejiang Cancer Hospital, Taizhou Hospital of Zhejiang Province, West China Hospital of Sichuan University, The Third Affiliated Hospital of Sun Yat-sen University, The First Affiliated Hospital of China Medical University, and The First

Affiliated Hospital of Xinxiang Medical University. Inclusion Criteria: All patients who underwent biopsy for focal pancreatic lesions, including US-guided FNA or CNB, EUS-guided FNA or FNB, to obtain cytological or histological specimens of the pancreas for pathological examination. Exclusion criteria: ① Patients with incomplete or missing case data (imaging, laboratory tests, pathological examinations); ② Patients with less than 12 months of clinical follow-up, lost to follow-up, or incomplete follow-up data; ③ Patients who underwent intraoperative biopsy; ④ Patients who underwent fluid aspiration procedures.

All EUS-FNA/FNB procedures were performed using a linear array echoendoscope (GF-UCT240, Olympus Medical Systems, Tokyo, Japan) and an ultrasound biopsy needle (Echotip, Cook Medical, Bloomington, USA). The biopsy needles included 25G, 22G, and 19G models, with the 22G FNA or FNB needle being the most widely used in our study. Under intravenous general anesthesia, the tip of the echoendoscope was inserted through the oropharynx into the gastric fundus, pylorus, and duodenum. After locating the target pancreatic lesion, the tip of the echoendoscope was fixed. For transgastric wall puncture, 25G, 22G, and 19G needles can be selected based on the type of lesion, surrounding tissue structure, and the operator's experience. When performing transduodenal wall puncture, considering the flexibility of the needle, 22G or 25G needles are chosen. Under endoscopic ultrasound guidance, if the FNA technique is used, the needle is inserted into the target lesion, and tissue or cells are obtained using the "slow pull" technique and negative pressure aspiration. The aspirated cell clusters are smeared and fixed with 95% alcohol for smear cytology examination; or placed in a liquid-based cell vial for liquid-based cytology examination. Simultaneously, the aspirated tissue is fixed in 10% formalin solution and sent for histopathological examination. When employing the FNB technique, the biopsy needle is inserted into the target lesion, and the lesion is excised using a specially shaped needle tip to collect tissue into the hollow core of the needle. After withdrawing the biopsy needle, the tissue is fixed in a 10% formalin solution. In this study, all cases utilized the Macroscopic On-Site Quality Evaluation (MOSE) technique, where the operator conducts an initial visual assessment of the extracted specimen. If the amount of tissue or cells obtained is insufficient for pathological evaluation, the biopsy procedure can be repeated until the specimen meets the pathological requirements. Preoperative and intraoperative use of Sonazoid (16ul/2ml, GE, USA) for contrast-enhanced ultrasound aids in assessing the blood supply within and around the target lesion. Sonazoid contrast agent is provided in lyophilized powder form and reconstituted with 2 ml of a specific solution to form a uniform microbubble suspension. A 2 ml bolus of this suspension is administered, followed by a 5 ml saline flush. The arterial phase enhancement process begins immediately after aortic enhancement, lasting 10 to 30

seconds, followed by the venous phase, which lasts 30 to 120 seconds. Routine archiving of imaging data is performed.

The ultrasound systems (Mindray, Shenzhen, China; Aloka, Tokyo, Japan; Esaote, MyLab 9, Florence, Italy) were equipped with ultrasound transducers (3.5 MHz convex array probes) for guiding and monitoring percutaneous pancreatic biopsy. The procedure was performed using CNB or FNA techniques. If the CNB technique was employed for tissue sampling, an automated core biopsy needle (18G and 16G, Magnum Bard, Covington, GA, USA) was used directly or guided by a coaxial needle; in FNA, a negative pressure aspiration biopsy needle (18G and 21G, HAKKO medical, Japan) was utilized. After preparing the skin, disinfecting, and draping at the puncture site, 1% lidocaine is used for layer-by-layer infiltration anesthesia at the intended puncture area. Under ultrasound guidance, an 18G fully automatic core biopsy needle is advanced to the anterior edge of the target pancreatic lesion, with the path options including direct, transgastric, or transhepatic routes. After activating the biopsy device, the specimen is retrieved and placed on filter paper, then promptly fixed in 10% formalin solution for histopathological examination. Typically, a single biopsy specimen measures 19mm in length and 1mm in width. If the sample is insufficient or the tissue appearance is inconsistent with pancreatic tumor, additional puncture biopsies can be immediately performed. If the FNA technique is used for sampling, an 18G or 21G puncture needle is inserted into the target pancreatic lesion. First, create negative pressure by pulling the device, then move the puncture needle up and down multiple times to obtain the specimen. The obtained cell clusters are smeared, then fixed in 95% alcohol for smear cytology examination. Meanwhile, the aspirated tissue strips are fixed in 10% formalin solution for histopathological examination. The operator conducts a preliminary macroscopic assessment of the retrieved specimens. If the specimen quantity is insufficient or its appearance does not match the disease, additional puncture biopsies can be performed until the specimen quantity meets the pathological requirements as assessed macroscopically. After puncture, routine examination of the puncture site and needle tract is necessary to early identify puncture-related complications. If signs of bleeding in the needle tract are observed, gelatin sponge can be inserted through the coaxial needle, or immediate compression hemostasis can be performed. Preoperative and intraoperative use of SonoVue (59 mg/vial, Bracco, Milan, Italy) or Sonazoid (16ul/2ml, GE, USA) for contrast-enhanced ultrasound (CEUS) aids in evaluating the blood supply within and around the target lesion. SonoVue contrast agent is provided in lyophilized powder form and reconstituted with 5 ml saline to form a uniform microbubble suspension. In use, 2.4 ml of this suspension is injected as a bolus, followed by a 5 ml saline flush. Sonazoid contrast agent is provided in the form of

lyophilized powder and is reconstituted with 2 ml of a specific solution to form a homogeneous microbubble suspension. A 0.5 ml bolus of this suspension is administered, followed by a 5 ml saline flush. The arterial phase enhancement process begins immediately after aortic enhancement, lasting for 10 to 30 seconds, followed by the venous phase, which persists for 30 to 120 seconds. Routine archiving of imaging data is performed.

The baseline data of enrolled patients were collected from the electronic medical record system, including the patients' names, genders, hospital admission numbers, examination numbers, puncture dates, and body mass index (BMI). Collect all imaging data (CT, MR, ultrasound, PET, and MRCP, etc.) of the patient on the integrated imaging system, and evaluate and record the imaging characteristics of focal pancreatic lesions. The indicators include the location of the lesion, which is divided into the head, uncinate process, neck, body, and tail; the size of the lesion, measured by the puncture operator and assistant on the maximum cross-section of the lesion displayed on the ultrasound image, with the average value recorded; and the exophytic retrograde morphology of the lesion, assessed by CT or MR. This term refers to the lesion morphology originating from the innermost edge of the pancreas and extending posteriorly beyond the pancreas, or presenting as a perivascular soft tissue sheath surrounding the superior mesenteric artery or celiac trunk, rather than a distinct mass. This is an atypical feature of common pancreatic lesions and is therefore easily overlooked. Information related to pancreatic puncture, including previous puncture history, imaging guidance method, puncture technique, needle gauge, puncture path, auxiliary techniques (contrast-enhanced ultrasound or coaxial technique), operator, post-puncture pathological results, complication status, and repeat puncture status, is collected and recorded by an assistant through the electronic medical record system.

After the puncture, follow-up education is provided to the patient, including a 12-month clinical follow-up. The follow-up encompasses surgical pathology results, repeat puncture pathology results, imaging examination results (CT, MRI, and ultrasound), laboratory test results (complete blood count, liver and kidney function, blood biochemistry, tumor markers, blood and urine amylase), and case records (outpatient and inpatient records).

The primary endpoint of this study was the inaccuracy of EUS- and US-guided pancreatic biopsy in diagnosing focal pancreatic lesions. Cases were classified as true positive results if the histopathological diagnosis post-biopsy was pancreatic ductal adenocarcinoma (PDAC), pancreatic neuroendocrine tumor (PNET), or other definitive malignant or benign pancreatic tumors, and if these findings were consistent with the results of at least

12 months of clinical follow-up (including medical history, laboratory tests, imaging studies, and pathological examinations). When post-puncture histopathological diagnosis indicates inflammation or an inconclusive result, further confirmation of the disease nature is required. If the biopsy results suggest inflammation or are inconclusive, but clinical and imaging evidence strongly indicate malignancy, a repeat biopsy or sampling is recommended. The necessity for repeated sample collection is determined through multidisciplinary discussion. For patients without indications for repeat biopsy, at least 12 months of clinical dynamic monitoring is required, including medical history, imaging (CT or MR), and tumor marker tests. Cases where the lesion size remains stable (diameter increase  $\leq 20\%$ ), exhibit imaging characteristics of benign lesions, and show no change in tumor markers are classified as benign. Cases with a diameter increase  $> 20\%$  and an absolute increase of more than 5 mm, along with an increase in tumor markers, are classified as malignant. Based on clinical follow-up of at least 6 months post-procedure, cases ultimately diagnosed as benign were considered true negative results, while those ultimately diagnosed as malignant were considered false negative results. The probability of diagnostic inaccuracy was the percentage of the sum of false positive and false negative cases out of the total number of cases. The secondary study endpoints were the incidence rates of severe complications, mild complications, and repeat biopsy after EUS and US-guided pancreatic biopsy. Post-procedure complications were assessed and graded according to the clinical practice guidelines of the Society of Interventional Radiology. Adverse events related to puncture occurring within 30 days post-operation fall under the category of complications. These include immediate post-puncture bleeding or hematoma, vagal reflex, infection, puncture-related pancreatitis, organ rupture (duodenum or colon), arteriovenous fistula, and arterial dissection.

Normally distributed measurement data are expressed as mean and standard deviation, while non-normally distributed measurement data are expressed as median and interquartile range (IQR). Categorical data are presented as percentages. For intergroup comparison of normally distributed measurement data, the t-test is used to assess differences; for non-normally distributed data, non-parametric tests are employed. Differences in intergroup categorical data are evaluated using the chi-square test or Fisher's exact test. Missing BMI values, which account for 0-12.7% of all data, are estimated using a random forest-based imputation technique. The propensity score matching (PSM) method was employed to control for confounding factors between the two groups, ensuring a balance of variables across them. PSM utilized a nearest-neighbor 1:1 matching approach with a caliper value set at 0.02. Before and after PSM matching, differences in study endpoints between the EUS-FNA/FNB and US-FNA/CNB groups were compared using chi-square or Fisher's exact tests. In addition to

analyzing the entire population, subgroup analyses were conducted based on lesion size, location, and morphology. A P-value of  $<0.05$  was considered statistically significant. Statistical analysis was conducted using SPSS software (version 26.0; IBM SPSS) and R software (version 4.2.3; R Development Core Team).

All records regarding the identity of enrolled patients are kept confidential and will not be disclosed outside the scope permitted by relevant laws and/or regulations.

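### A 12-month follow-up requirement with no provision for death governs the 30-day complication endpoints; read literally, a complication that is fatal before month 12 cannot be counted

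*Protocol*

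**What the plan says.** In the Protocol section, exclusion criterion ② removes "Patients with less than 12 months of clinical follow-up, lost to follow-up, or incomplete follow-up data". Short follow-up and loss to follow-up are listed as separate grounds, and death is not mentioned there or elsewhere. The paragraph on follow-up says that "follow-up education is provided to the patient, including a 12-month clinical follow-up".

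The endpoint paragraphs name the secondary outcomes: "The secondary study endpoints were the incidence rates of severe complications, mild complications, and repeat biopsy after EUS and US-guided pancreatic biopsy". The window for complications is short: "Adverse events related to puncture occurring within 30 days post-operation fall under the category of complications".

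The statistical paragraph states that, before and after matching, "differences in study endpoints between the EUS-FNA/FNB and US-FNA/CNB groups were compared". It also refers to "analyzing the entire population, subgroup analyses were conducted based on lesion size, location, and morphology". It names no separate cohort for complications.

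The reference standard for the primary endpoint carries two follow-up lengths. For inflammatory or inconclusive results: "For patients without indications for repeat biopsy, at least 12 months of clinical dynamic monitoring is required". A few sentences later: "Based on clinical follow-up of at least 6 months post-procedure, cases ultimately diagnosed as benign were considered true negative results". The definition of a true positive also asks for agreement with at least 12 months of follow-up.

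**The concern.** Twelve months of follow-up serves the diagnostic endpoint, where the final diagnosis may need time to declare itself. It has no role in an outcome that is fully observed at day 30. Because criterion ② acts at eligibility, it conditions the complication, repeat-biopsy and inaccuracy results alike on what happened to the patient after the biopsy.

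Three things are at stake.

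- **Fatal complications.** Comparing complication rates is part of the stated objective. On the literal reading, the most serious events are the ones the study cannot record.
- **Precision.** The Background describes adverse events as uncommon. Discarding fully observed 30-day outcomes wastes information where it is scarcest.
- **Interpretation.** If deaths are excluded, the inaccuracy rate describes only patients alive at 12 months. Propensity matching on baseline variables cannot bring back patients removed for post-biopsy events.

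Separately, the 6-month threshold for true and false negatives conflicts with the 12-month requirement stated just before it. Under criterion ② it can never operate, since everyone retained has 12 months.

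**Working it through.** The protocol states no sample size, event count, mortality, case mix, miss rate or complication rate, so there is no figure to reproduce. The core of the check is logical; the arithmetic only gives scale.

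**Logic.** A patient who dies at time t < 12 months has less than 12 months of follow-up and so meets criterion ②. If the death followed a complication within 30 days, that complication is not counted. Only a 30-day complication leading to death after month 12 would still be seen. Substituting the 6-month figure would not rescue a death within 6 months. A survivor whose records stop between day 30 and month 12 is also removed, however deaths are treated.

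**Assumed inputs (none from the protocol).** Per 100 biopsied: M = 70 or 80 malignant, B = 100 − M benign; 12-month mortality m = 0.2 to 0.5 in malignant and 0.05 in benign cases; a fraction f of malignancies missed; no false positives. The exclusion shares below apply only if deaths are excluded.

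**Share excluded** = M·m + 0.05·B (per 100)

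| m | M = 70 | M = 80 |
|---|---|---|
| 0.2 | 14 + 1.5 = 15.5 | 16 + 1 = 17 |
| 0.3 | 22.5 | 25 |
| 0.4 | 29.5 | 33 |
| 0.5 | 35 + 1.5 = 36.5 | 40 + 1 = 41 |

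**Complications, leaving unrelated to complications.** Of 10 expected severe events, 10 × 0.845 = 8.45 remain at 15.5% excluded and 10 × 0.59 = 5.9 at 41%. The standard error grows by 1/√(1 − e): 1/√0.845 = 1.088 and 1/√0.59 = 1.302. There is no bias in this case. The factor holds for any excluded share e, whatever the reason for leaving.

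**Complications, a share φ of severe events fatal before month 12**, non-fatal cases leaving like everyone else: observed rate = p(1 − φ)/(1 − pφ).

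- p = 1%: 1.00% (φ = 0), 0.95% (φ = 0.05), 0.90% (φ = 0.10), 0.80% (φ = 0.20).
- p = 2%, with larger fatal shares: 1.80% (φ = 0.10), 1.51% (φ = 0.25), 1.01% (φ = 0.50).
- The number of such fatal events counted is zero throughout.

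**Complications, non-fatal cases leaving at a different rate.** Take 1,000 patients with 10 events, where 30% of the other 990 leave and 693 remain. If 40% of event cases leave, 6/(6 + 693) = 0.86%. If 20% leave, 8/(8 + 693) = 1.14%. The true rate is 1.0%.

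**Inaccuracy, death unrelated to the biopsy result:** f·M(1 − m)/[M(1 − m) + 0.95·B], with f = 0.10. True values are 7% (M = 70) and 8% (M = 80).

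| m | M = 70 | M = 80 |
|---|---|---|
| 0.2 | 5.6/84.5 = 6.63% | 6.4/83 = 7.71% |
| 0.3 | 6.32% | 7.47% |
| 0.4 | 5.96% | 7.16% |
| 0.5 | 3.5/63.5 = 5.51% | 4/59 = 6.78% |

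With equal mortality in the two arms the spurious difference is 0. With a 10-point mortality difference it is 0.24–0.45 percentage points at f = 0.10, 0.12–0.22 at f = 0.05 and 0.37–0.67 at f = 0.15.

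**The case against.** The strongest objection is that criterion ② does not mention death. Follow-up is described as a set of records (pathology, imaging, laboratory results, case notes), and a site could treat records complete to death as complete follow-up. That reading is possible, and under it the exclusion shares above do not apply. But the wording points the other way: short follow-up is a ground of its own beside loss to follow-up, and the true-positive definition also asks for 12 months. The protocol does not settle the matter. The point about survivors with records ending between day 30 and month 12 does not depend on it.

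Second, the phrase about the entire population mainly contrasts the whole cohort with subgroups and does not prove a single denominator. That is fair, and the phrase is weak support. The argument rests on ② being a study-level exclusion with no separate complication cohort defined. For the same reason an analysis plan that is not shown would not easily restore patients the protocol excludes.

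Third, no bias in the comparison is shown, and every numerical input is assumed. Both statements stand. The EUS–US contrast is distorted only if early exit differs by arm or relates differently to the outcome, and the protocol gives nothing from which to judge size or direction.

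Fourth, the 6- versus 12-month conflict is a separate matter without numerical consequence under ②. It is secondary and adds no weight to the main point, but it concerns the primary endpoint's reference standard and needs correcting.

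**Conclusion.** The concern holds and should be fixed. Certain from the text: a 12-month requirement governs entry to a 30-day endpoint, the handling of deaths is unstated, and the 6- and 12-month figures conflict. Conditional on the literal reading: complications fatal before month 12 cannot appear in either group, and the severe-complication rate is understated if any are fatal and non-fatal cases leave like other patients.

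On the assumed inputs the main loss is in the safety endpoints, through fewer counted events, a larger standard error and missing fatal cases. The likely effect on the accuracy contrast is small. Bias in the EUS–US comparison is possible but not demonstrated. Confidence is medium, because the point about deaths turns on a reading the protocol leaves open.

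**What to change.** 1. Analyse the 30-day complication endpoints in all otherwise eligible biopsied patients who have 30-day records or died within 30 days, and rerun the matching on that cohort.
2. State in criterion ② that follow-up ending in death is not a reason for exclusion when records to death are complete. Align the 12-month wording of the true-positive definition, and say how a negative or inconclusive case that dies before 12 months is classified.
3. Reconcile the 6- and 12-month figures across the exclusion criteria and the endpoint definitions.
4. Keep the 12-month rule for all other cases in the primary inaccuracy analysis. Add a sensitivity analysis that also keeps patients whose final diagnosis was settled earlier by surgical or repeat-biopsy pathology, noting that inclusion then depends partly on the diagnosis.

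The cost is wording changes, extra record review and a second matching run. There are downsides. Safety and accuracy will rest on different cohorts. Some patients who die early will lack the imaging and marker data needed to classify them. The sensitivity analysis can shift the case mix. If the data are already assembled, the change should be labelled as made after data collection.

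### A routine post-puncture complication check is described for the US arm only, so recorded rates of minor immediate bleeding may not be comparable between US and EUS

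*Protocol*

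**What the plan says.** All of the text concerned is in the section headed Protocol.

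- **US procedure.** After the sampling steps: "After puncture, routine examination of the puncture site and needle tract is necessary to early identify puncture-related complications". The next sentence gives the response to a positive finding: "If signs of bleeding in the needle tract are observed, gelatin sponge can be inserted through the coaxial needle, or immediate compression hemostasis can be" carried out.
- **EUS procedure.** Once the needle is out, the account turns to the specimen: "After withdrawing the biopsy needle, the tissue is fixed in a 10% formalin solution". The only on-site evaluation described is of specimen quality, where "the operator conducts an initial visual assessment of the extracted specimen". The rest covers repeat sampling, contrast use and image archiving. No examination for complications is mentioned.
- **Endpoints.** "The secondary study endpoints were the incidence rates of severe complications, mild complications, and repeat biopsy after EUS and US-guided pancreatic biopsy". The list of countable events opens with bleeding: "These include immediate post-puncture bleeding or hematoma, vagal reflex, infection, puncture-related pancreatitis".
- **Rules common to both arms.** The window is 30 days: "Adverse events related to puncture occurring within 30 days post-operation fall under the category of complications". There is one grading system: "Post-procedure complications were assessed and graded according to the clinical practice guidelines of the Society of Interventional Radiology". Complication status is abstracted from the electronic medical record in both arms.
- **Analysis.** Endpoints are compared between arms by chi-square or Fisher's exact test, before and after 1:1 propensity score matching.

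**The concern.** A minor bleed that causes no symptoms is counted only if someone looks, sees it and writes it down. The Protocol describes a deliberate look after US puncture and none after EUS puncture, and it sets no common rule for ascertaining immediate bleeding. The first event on its complication list is the one such a look would reveal. A difference in recorded mild complications could then partly reflect how closely each arm was examined, and readers would take it as a difference in safety. Propensity score matching does not help: it balances characteristics present before the procedure, whereas detection belongs to the procedure itself.

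**Working it through.** **Step 1. The passages side by side**

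| Item | US | EUS |
|---|---|---|
| Check for complications after puncture | Described as routine and necessary | None described |
| Response to tract bleeding | Described | None described |
| On-site evaluation | Specimen, plus puncture site and tract | Specimen only |
| Immediate bleeding or haematoma counts | Yes | Yes |
| Window, grading, data source | 30 days, one guideline, medical record | The same |

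The arms differ in how an immediate bleed would come to notice. They do not differ in how a noticed and recorded bleed is graded or abstracted.

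**Step 2. What could be affected**

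The Protocol states no complication rate, event count or sample size, so there is no figure to reproduce. Everything below is illustrative, and all rates, detection shares and sample sizes are assumptions.

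**Step 3. Effect on the bleeding component**

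Take the same true rate p of minor bleeding in both arms, full detection after US and a share s detected after EUS. Let h be the share of recordable US bleeds that immediate haemostasis keeps out of the record. Then

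recorded ratio US/EUS = p(1 − h) / (p·s) = (1 − h)/s.

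| s | h = 0 | h = 0.2 | h = 0.5 |
|---|---|---|---|
| 1.0 | 1.00 | 0.80 | 0.50 |
| 0.8 | 1.25 | 1.00 | 0.62 |
| 0.5 | 2.00 | 1.60 | 1.00 |

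The ratio lies above or below 1 depending on s and h, and the Protocol gives neither.

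**Step 4. Chance of a falsely significant difference when h = 0**

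This uses a two-proportion z-test with pooled variance under the null and two-sided alpha 0.05 (the Protocol gives 0.05 without stating sidedness). Worked case with p = 0.05, s = 0.5 and 500 per arm:

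- recorded rates 0.05 and 0.025, difference 0.025, mean 0.0375
- null standard error √(2 × 0.0375 × 0.9625 / 500) = 0.01202
- alternative standard error √((0.05 × 0.95 + 0.025 × 0.975) / 500) = 0.01199
- (1.96 × 0.01202 − 0.025) / 0.01199 ≈ −0.12, so the chance is about 55%

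| p | s | n = 200 | n = 500 | n = 1000 per arm |
|---|---|---|---|---|
| 2% | 0.8 | 6.0% | 7.6% | 10.3% |
| 2% | 0.5 | 13.0% | 25.5% | 45.2% |
| 5% | 0.8 | 7.7% | 11.9% | 19.0% |
| 5% | 0.5 | 26.0% | 54.8% | 83.8% |
| 10% | 0.8 | 10.7% | 19.7% | 34.6% |
| 10% | 0.5 | 47.5% | 85.2% | 98.9% |

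With s = 1 every entry is 5%. The normal approximation is rough where events are few; Fisher's exact test would reject less often there.

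**Step 5. Effect on the whole mild-complication rate**

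Suppose 3% of patients in each arm have clinically evident mild events and a further 5% have bleeding visible only on an immediate check, with h = 0:

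- US: 3 + 5 × 1.0 = 8%
- EUS, one in five found: 3 + 5 × 0.2 = 4%
- EUS, four in five found: 3 + 5 × 0.8 = 7%
- EUS, all found: 3 + 5 × 1.0 = 8%

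If none of the check-only bleeds needed treatment, excluding them gives 3% against 3% in every case.

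**The case against.** The strongest reply is that this argues from silence. The two procedure paragraphs describe technique and are not rules for finding complications. The EUS paragraph does not say that cases went unchecked, and the puncture itself was done under ultrasound vision with contrast available to assess blood supply. That stands. A reader might infer that EUS patients were not examined, and the document does not support this.

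A second tempting inference is that the comparison is biased against US. This is not shown either. Nothing says that a bleed seen only at the US check is entered as a complication. The check also leads to haemostasis, which could prevent a later haematoma and so lower the US count. The counter-argument has some force: haemostasis follows a bleed already seen, so it lowers the count only if treated bleeds go uncoded or if recording depended on progression. Over-recording after US is therefore the more natural reading, but it remains unproven.

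A third reply is that the common 30-day window, grading guideline, record source and follow-up imaging and laboratory tests equalise the arms. They do so for events that produce symptoms or leave a later trace. They cannot recover a small bleed that resolved unseen.

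Finally, removing check-only bleeds from the tested endpoint would discard events that the Protocol expressly lists, including US bleeds that needed haemostasis, and could favour US. This is accepted, and the fix below leaves the listed endpoint intact.

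**Conclusion.** The concern holds in limited form. The Protocol describes active post-puncture detection in one arm only, sets no common ascertainment rule, and compares an endpoint containing the event that such detection would reveal. Recorded mild-bleeding rates may therefore not be comparable.

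The size cannot be derived from the document. Under the assumptions shown, with no effect of haemostasis, the recorded ratio for bleeding runs from 1.00 (equal detection) through 1.25 to 2.0 against US. Allowing for haemostasis, it can reach 1 or fall below it. A spurious doubling is one assumed scenario and not an estimate.

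The problem is confined mainly to immediate minor bleeding within a secondary endpoint. Diagnostic inaccuracy, the primary endpoint, does not depend on it. Severe complications should come to notice in either arm within 30 days, so they are little affected. The matter should be put right, but it does not threaten the study's main conclusion.

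**What to change.** 1. Keep the mild-complication endpoint as the Protocol lists it.
2. At abstraction, code for each bleed or haematoma whether it was seen only on the immediate post-procedure check, and whether it needed haemostasis. Allow an unclear category.
3. Report check-only bleeds in a separate row for each arm.
4. Pre-state a sensitivity comparison of mild complications that excludes check-only bleeds needing no treatment. Events with symptoms, a laboratory change, a later imaging finding or an intervention stay in.
5. State what post-procedure check the EUS records document. If it was equivalent to the US check, one sentence largely settles the matter.
6. Interpret a difference in mild complications as a difference in safety only if it persists in the sensitivity comparison, judged on the estimate and its interval as well as the P-value.

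The cost is small: added coding of bleeding events in records that are being abstracted anyway, some records across the seven hospitals where the mode of detection cannot be determined, and fewer events, hence less precision, in the sensitivity comparison. One limit remains: a US bleed found at the check and treated stays in, while a similar unseen EUS bleed would not be counted. The haemostasis code lets readers see how many such cases there are.
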